### 2.2 Objectives

**Primary objective** is to evaluate whether a diagnostic strategy using **LDCT** compared with **CXR** leads to a more accurate diagnosis in elderly patients with suspected pneumonia in the emergency room (ER). We hypothesise that an **LDCT-based diagnostic strategy** will have better accuracy than the standard of care **CXR-based strategy** for the diagnosis of pneumonia in elderly patients admitted to the ER.

#### Secondary objectives

To assess the difference in diagnostic performance and clinical outcomes for patients with suspected pneumonia using LUS compared to CXR, and using LUS compared to LDCT.

### 3. Study methods

#### 3.1 Design

##### **Swiss multicentre superiority randomized clinical study with 3 parallel arms.**

Involved centres were Geneva, Bern, Lugano

Each patient was randomly allocated in the ER to one of the three imaging examination (CXR, LDCT or LUS). Imaging examination was immediately performed, interpreted by one independent radiologist (CXR)

radiologist (LDCT) – different from the radiologist interpreting (CXR)

trained emergency physician (LUS)-different from the physician in charge of the patient

The **physician in charge** of the patient had access to the imaging examination and the corresponding report, in addition to usual clinical and biological data obtained in the diagnostic workup of suspected pneumonia; he/she **was asked to assess the probability of pneumonia before the patient is discharged from the ER**.

For each patient, **the other two imaging examinations were also performed** and interpreted as described above, **but the physician in charge of the patient was blinded to these results**.

The 3 imaging examinations were performed within the first hours of ER admission.

#### 3.2 Randomization

Patients were randomised immediately after inclusion in one of the three arms (CXR, LDCT, LUS). Randomisation was performed using REDCap tool with a 1:1:1 ratio, stratified by centre and using permuted block sizes of 3 or 6.

#### 3.3 Outcomes

We present here a summary of the study outcomes. For detailed definitions of the outcomes, see chapter [8.1 Outcome definitions](#).

##### 3.3.1 Primary outcome

The primary outcome is the **accuracy** of the clinician's diagnosis using the experts' diagnosis as reference.

##### 3.3.2 Secondary outcomes

The following **additional diagnostic performance measures** were planned to be evaluated

- Sensitivity (Se)
- Specificity (Sp)
- Positive Predictive Value (PPV)
- Negative Predictive Value (NPV)
- Positive Likelihood Ratio (PLR)
- Negative Likelihood Ratio (NLR)

Secondary outcomes consisted in diagnosis, treatment and clinical outcomes.

#### Diagnosis outcomes

- Unmasked imaging modalities in emergency
- Alternative diagnoses
- Diagnosis of aspiration pneumonia (yes/no)
- Type of pneumonia (viral/bacterial)
- Additional imaging studies ordered

#### Treatment outcome

- Antibiotic free days

#### Clinical outcomes

- Time to clinical stability
- Hospital admission
- Length of hospital-stay
- ICU admission
- Transfer to rehabilitation or long-term care facility (LTCF)
- All-cause ICU readmission
- In-hospital mortality
- All-cause mortality at 30 days and at 90 days
- Quality of life at 30 days and at 90 days

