3.2 Primary and secondary endpoints

Primary outcome measure:

The primary outcome will be the difference in accuracy between LDCT and CXR, assessed at the end of the ED evaluation, using the expert panel as the reference standard, accuracy being computed as (true positive + true negative cases) / (true positive + true negative + false positive + false negative cases).-

Main secondary outcome measures:

Diagnostic outcomes:

- Difference in accuracy between LUS and CXR, assessed at the end of the ED evaluation, using the expert panel as the reference standard
- Sensitivity, specificity of CXR, LDCT and LUS
- Number of additional imaging studies and invasive procedures prescribed during the acute setting
- Prevalence of viral pneumonia
- Prevalence of unmasked imaging results (for an emergency finding)
- Prevalence of incidentalomas

Treatment outcomes:

- Number of antibiotic free days at day 30

Clinical outcomes:

- Time to clinical stability during the first 2 weeks (number of days from admission to the first time all of the following parameters are above/under the threshold value and maintained for a minimum of 24 hours: heart rate <100 beats/min, systolic blood pressure >90 mmHg, temperature <37.8°C (axillary or tympanic), respiratory rate <24 breath/min, oxygen saturation >90% while breathing room air, or need for more than 28% fraction of inspired oxygen to maintain adequate oxygen saturation, resolution of delirium if present at admission)
- Length of hospital stay (in the ED and in the acute setting)
- Proportion of patients with an unplanned transfer to the ICU
- Proportion of patients admitted to rehabilitation or LTCF days through 3 months
- All-cause mortality through 1 month and 3 months
- All-cause readmission to the acute care setting through 1 month and 3 months
- Quality of life at admission, discharge and 3 months (measured by EQ-5D-3L and a CAP score questionnaire)
 - Interagreement rate for the probability of pneumonia between physicians participating to the trial and a consensus of experts in chest imaging, for each method

- Association between biological markers (CRP and PCT) and the presence of an infiltrate

Cost outcomes:

Costs of care, physician, imaging, laboratory, treatment (including antibiotic therapy) and others per patient, health related quality of life until 3 months; unit of work consumption per hospital (number of minutes of care, physician, laboratory and imaging points)

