8) Clinical outcomes: We will use Kaplan Meier's estimates to evaluate the time to clinical stability over 15 days in each arm, and a log-rank to compare them. Patients who die in the first 2 weeks will be censored at day 15 (i.e. considered has never reaching clinical stability). The Mann-Whitney test will be used to compare the length of hospital stay between the groups. The proportion of patients with an unplanned transfer to the ICU or operating room will be reported by arm and compared between the arms using a logistic regression model adjusted for sites. All-cause mortality during the 3-month follow-up will be investigated with Kaplan Meier's survival curves, and compared between the arms using a log-rank test stratified on sites. Readmissions during the 3-month follow-up will be investigated using survival models with competing risk. Death before readmission will be the competing event.

9) Cost outcomes: Mean cost per patient will be assessed and compared between arms using multiple linear regression models adjusted for sites. Reweighted estimators will be used to account for censoring.

10) Interagreement rate for the probability of pneumonia rated on a 3-level Likert scale: the agreement between raters participating to the trial and a consensus of two experts will be investigated by using kappa statistics.

11) The association between biological markers (CRP and PCT) and infiltrates will be assessed by differences in the mean levels of markers between patients with and without infiltrates and tested by using t test. Transformations on markers will be applied if needed. Multiple linear regression models will be used for adjustment. Similar methods will be used to investigate the association between markers and the probability of pneumonia rated on the 3-level scale. The analyses will be conducted for each arm.

Interim and safety analyses

There will be no comparative analysis for efficacy or futility. An initial safety analysis will be performed after 200 patients have reached the 1-month follow-up. The study's data manager will ensure that the data will be exported with "scrambled" allocation labels and that study investigators do not have access to the data. The results will be transmitted to the principal investigators and the safety monitoring board. The latter will be free to lift the blind if deemed necessary, and will be asked to make the final decision on the continuation of the study without modification, or terminating the study.

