### 3.4 Timing of outcome assessments (timepoints)

Study periods	Timeline of patient enrolment/allocation, interventions and assessments						
	Screening	Randomisation	Discharge from ER	Discharge from the acute setting	Day 30	Day 90	Reference diagnosis
Visit	1	2	3	4	5	6	7
Time (hour, day)	hr0	hr2*	hr6*	dx	d30	d90	
Demographics	x						
Medical history	x						
Inclusion/exclusion criteria	x						
Physical examination	x						
Vital signs	x						
Laboratory tests	x			x			
CXR, LDCT, LUS		x					
Main diagnosis before ER discharge			x				x
Other diagnosis outcomes		x		x			x
Number of antibiotic free days					x		
Clinical, safety and cost outcomes			x		x		
Readmission and mortality					x	x	
QoL questionnaire			x		x	x	
Panel of experts							x

\*Approximately.  
CXR, chest x-ray; d, day; ER, emergency room; hr, hour; LDCT, low-dose CT; LUS, lung ultrasonography; QoL, quality of life.

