#### **Exclusion criteria:**

1. Need for an immediate admission to the intensive care unit (ICU)
2. Diagnosis of pneumonia in the past 3 months
3. SARS CoV-2 infection diagnosed by PCR or antigenic test within the past 3 weeks
4. Transfer from another hospital with a diagnosis of pneumonia
5. Thoracic CXR or CT scan or US already performed during the present episode
6. Need for an immediate contrast-enhanced CT
7. Advanced care planning limiting therapy to comfort care only
8. Prisoners
9. Known uncontrolled psychiatric disorders
10. Previous enrolment into the current study

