- **All-cause mortality within 30 days** will be defined as a death date (*death\_date* or *deathdate*) occurring within **30 days** of the emergency entry date (*emergencydate*)

- **All-cause mortality within 90 days** will be defined as a death date (*death\_date* or *deathdate*) occurring within **90 days** of the emergency entry date (*emergencydate*)

- **In-hospital mortality** will be defined as a death occurring on or before the hospital discharge date (*hospital\_discharge\_date*), based on the recorded death date (*death\_date* or *deathdate*)

- **All-cause readmission within 90 days** after initial emergency admission/evaluation will be defined as a readmission date (*readmission\_date*) occurring within **90 days** of the emergency entry date (*emergencydate*)

- **Quality-of-life at 30 days and 90 days** (*eq5d\_score*)

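### SAP 3.3.2 mislabels the readmission outcome, and the SAP omits the protocol's 1-month time point and competing-risk method for readmission without declaring either change

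*SAP*

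**What the plan says.** **Protocol.** Section 3.2 and the synopsis both list "All-cause readmission to the acute care setting through 1 month and 3 months". The separate ICU outcome in section 3.2 is "Proportion of patients with an unplanned transfer to the ICU", and no ICU readmission outcome appears anywhere. For the analysis, section 5.1 states: "Readmissions during the 3-month follow-up will be investigated using survival models with competing risk". It names death before readmission as the competing event.

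**SAP.** Section 3.3.2 lists "All-cause ICU readmission" and contains no acute-care readmission entry. Section 8.1.2.4 defines "All-cause readmission within 90 days", counted from the emergency entry date and not restricted to the ICU. Section 8.2.3.4 describes acute-care readmission from any cause by arm, as counts and percentages in patients discharged alive. It gives no time point and says that the arms will not be compared. The schedule in section 3.4 has a row "Readmission and mortality" marked at both day 30 and day 90. In section 9, the list of protocol analyses that will not be done has one item, time to clinical stability.

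**The concern.** The SAP names one readmission outcome in its summary list and analyses a different one. Neither includes the protocol's 1-month readmission. Anyone building tables or checking the final report from section 3.3.2 would look for an ICU result that section 8 does not produce, and would not find the protocol's outcome in the list.

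SAP section 1 says that the SAP was finalised after enrolment and before analysis, and that it covers only the analyses it describes. It defers the ancillary studies, costs and the biomarker analysis to a separate plan, but not readmission. Followed as written, the SAP would leave a secondary outcome named in the protocol unreported at one of its two time points and analysed by a different method at the other, with no record of either decision. An undeclared change made after enrolment invites questions about selective reporting. Declaring it before analysis removes most of them.

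**Working it through.** No figure in the plan bears on this point, so the check is a comparison of the texts.

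| Element | Protocol | SAP |
|---|---|---|
| Name in the outcome list | Acute-care readmission, any cause (synopsis, 3.2) | ICU readmission, any cause (3.3.2) |
| Definition | Acute-care readmission | Any readmission date, not ICU-specific (8.1.2.4) |
| Time points | 1 month and 3 months | 90 days (8.1.2.4); none stated (8.2.3.4); day 30 and day 90 in the schedule (3.4) |
| Patients | No restriction stated | Those discharged alive (8.2.3.4) |
| Method | Competing-risk survival models (5.1) | Counts and percentages (8.2.3.4) |
| Comparison of arms | Difference between strategies is a stated objective (3.1) | None (8.2.3.4) |
| Change declared | – | Not in section 9 |

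**Step 1: the label.** ICU readmission appears once in the SAP, in 3.3.2, and has no counterpart in 8.1 or 8.2. ICU admission is a separate entry in the same list, and section 8 covers it as transfer to the ICU/IMCU within 30 days. The readmission entry is therefore not a variant of the transfer outcome. The definition in 8.1.2.4 and the wording in 8.2.3.4 both match the protocol's acute-care outcome, so a mislabelled entry is the simplest explanation.

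**Step 2: the 1-month time point.** SAP 8.1.2.4 defines mortality at both 30 and 90 days and names quality of life at both. Readmission alone has only the later time point. The rule there is a readmission date within 90 days of the emergency entry date, so a 30-day version needs the same two variables and a different cut-off.

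**Step 3: the method.** Under the protocol, a patient who dies before readmission has a competing event and stays in the risk set up to that point. A cumulative incidence curve over 3 months could also be read at 1 month. Under the SAP, in-hospital deaths leave the denominator. The SAP does not say how it treats death after discharge and before readmission, or incomplete follow-up, beyond the general complete-case rule in 8.4. Protocol 4.4 instead censors patients lost to follow-up.

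The two summaries estimate different quantities. Let *n* be the patients in an arm, *h* the proportion who die in hospital, and *R* the number readmitted by day 90. With complete follow-up, the protocol's cumulative incidence is *R/n* and the SAP's percentage is *R/[n(1 − h)]*. They agree only if *h* = 0. The documents give no value for *h*, so the gap cannot be sized. Because the denominator depends on survival after randomisation, arms that differ in *h* would no longer be strictly comparable even descriptively.

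**Step 4: the declaration.** Section 9 mentions neither the missing time point nor the change of method.

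**The case against.** The strongest reply is that little of substance is lost. SAP 3.3 calls itself a summary and sends the reader to 8.1 for definitions, so the stray label is resolved inside the SAP and nothing would be computed under it. The objective in protocol 3.1 refers to readmission up to 3 months, and protocol 5.1 sets out no separate 1-month analysis. The relevant list in section 9 covers analyses, so an outcome that never had its own analysis arguably does not belong there. Events by day 30 are contained in the 90-day count. In 8.2.3.4 the neighbouring rehabilitation and long-term care entries specify 3 months, so 90 days can be inferred for readmission.

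The argument about the label stands: it is an editorial correction. The rest stands only in part. The synopsis and section 3.2 both name the 1-month outcome, and the synopsis objectives mention 1-month readmission. A single 90-day percentage cannot be broken down to day 30, whereas the planned competing-risk analysis could be read there. The argument about section 9 does not cover the method, because the competing-risk model is an analysis that protocol 5.1 specifies.

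A reader might also infer that the SAP replaced a common outcome with an ICU outcome that will have almost no events. The documents do not support this. Section 8 keeps acute-care readmission, the exclusion criterion covers only patients who need the ICU immediately, and no ICU or readmission rate is given.

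**Conclusion.** The point holds as a minor inconsistency in secondary-outcome reporting. It has three parts: a wrong label in SAP 3.3.2; a 1-month readmission outcome with no definition or analysis; and an undeclared move from competing-risk models to uncompared counts in patients discharged alive. The third is the most substantive.

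The primary outcome and its error control are not affected. The effect on the readmission results cannot be put in numbers, because the documents give no readmission or in-hospital death rate. The conclusion rests on the wording alone. Calling the ICU entry a labelling error is an inference, though section 8 supports it strongly.

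A reader might further infer that day-30 readmission data have been abandoned or a result deliberately withheld. Neither follows. Collection at day 30 is still scheduled, readmission is recorded as a date, and the SAP states that it was finalised before analysis began.

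**What to change.** 1. In SAP 3.3.2, replace the ICU readmission entry with acute-care readmission from any cause at 30 and 90 days.
2. In 8.1.2.4, add a 30-day definition beside the 90-day one, using `readmission_date` and `emergencydate`. State that time is counted from emergency entry for both, so that days still in hospital fall inside the window.
3. In 8.2.3.4, report both time points by arm, preferably as cumulative incidence with death before readmission as the competing event, as protocol 5.1 planned. State how incomplete follow-up is handled.
4. If the descriptive counts are kept, or the 30-day time point is dropped, declare in section 9 the change of method, the restriction to patients discharged alive, the absence of a comparison between arms and any dropped time point, with reasons.

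The cost is a few lines of SAP text and one more row in the clinical outcomes table. The competing-risk option adds one standard analysis. No new data are needed, and the change should be made before the database is locked.

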### 3.4 Timing of outcome assessments (timepoints)

Study periods	Timeline of patient enrolment/allocation, interventions and assessments						
	Screening	Randomisation	Discharge from ER	Discharge from the acute setting	Day 30	Day 90	Reference diagnosis
Visit	1	2	3	4	5	6	7
Time (hour, day)	hr0	hr2*	hr6*	dx	d30	d90	
Demographics	x						
Medical history	x						
Inclusion/exclusion criteria	x						
Physical examination	x						
Vital signs	x						
Laboratory tests	x			x			
CXR, LDCT, LUS		x					
Main diagnosis before ER discharge			x				x
Other diagnosis outcomes		x		x			x
Number of antibiotic free days					x		
Clinical, safety and cost outcomes			x		x		
Readmission and mortality					x	x	
QoL questionnaire			x		x	x	
Panel of experts							x

\*Approximately.  
CXR, chest x-ray; d, day; ER, emergency room; hr, hour; LDCT, low-dose CT; LUS, lung ultrasonography; QoL, quality of life.

### 3.5 Sample size, null and alternative hypothesis

**The final recruitment objective was 165 patients in each arm, for a total of 495 patients.**

The sample size calculation was based on the following hypotheses: based on the PneumO-LD-CT cohort, the expected accuracy of the clinician's diagnosis is 68% when based on CXR and 84% when based on LDCT. With an expected improvement of 16% of the accuracy using LDCT instead of CXR, 150 patients will be required in each arm to demonstrate the superiority of LDCT over CXR with a two-sided alpha error of 0.05 and a power of 90%. Allowing for a 10% drop-out after randomisation, the final recruitment objective is 165 patients in each arm, for a total of 495 patients.

**Null hypothesis:** the proportion of accurate clinician's diagnosis is the same on CXR and LDCT.

**Alternative hypothesis:** the proportion of accurate clinician's diagnosis is different between CXR and LDCT.

### 3.6 Interim analyses and stopping rules

There was no interim analysis for efficacy or futility. An initial safety analysis was planned after 200 patients have reached the 1-month follow-up. The safety monitoring board was free to make the final decision on the continuation of the study or terminating the study. The safety monitoring board did not decide on terminating the study.

### 3.7 Timing of final analysis

All outcomes collected up to 90 days will be analysed after study completion and expert adjudication. Following the completion of data entry, data validation and cleaning will be performed. Data analysis will start after the database has been locked.

### 3.8 Blinding

All three imaging examinations were performed for each patient:

- **CXR** was interpreted by **an independent radiologist**
- **LDCT** was interpreted by **a second independent radiologist**, different from the one who interpreted the CXR
- **LUS** was interpreted by **an independent ultrasonographer**

#### **Physician in charge**

The treating physician was aware of the allocation group. However, he was blinded to the results of the two non-assigned radiological examinations, which were concealed for 5 days. The examinations to be masked were known to the research staff immediately after randomisation. Emergency unblinding was permitted in the occurrence of an immediately life-threatening finding (see Box 2).

#### **Panel of experts**

The panel of experts was consulted only after the completion of patient recruitment and had access to all data (clinical information and outcome data), including the results of all radiological examinations (CXR, LDCT, and LUS). However, each expert was blinded to the allocation group and to the final evaluation made by the physician in charge (published in ClinicalTrials.gov).

## Box 2 Reasons for emergency unblinding

- ⇒ Pneumothorax.
- ⇒ Haemothorax.
- ⇒ Indirect signs of aortic dissection.
- ⇒ Indirect signs of aneurysmal rupture (haemomediastinum).
- ⇒ Massive pericardial effusion.
- ⇒ Tracheal foreign body.
- ⇒ Pneumoperitoneum.
- ⇒ Pneumomediastinum.
- ⇒ Malignant airway obstruction.
- ⇒ Suspected acute tuberculosis.

## 4. Statistical principles

### 4.1 Significance level, confidence interval, multiple testing

All statistical tests will be two-sided at the significance level of 0.05.

### 4.2 Analysis populations

In this document the term 'full analysis set' is used to describe the analysis set which is as complete as possible and as close as possible to the intention-to-treat ideal of including all randomised subjects.

#### 4.2.1 Full analysis set (FAS)

The full analysis set will include all randomized patients, except those who met one of the following criteria:

- *the failure to satisfy major entry criteria (eligibility violations)*
- *the failure to undergo any of the trial exams*
- *the lack of any data post randomization*

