4. STUDY POPULATION AND STUDY PROCEDURES

4.1 Inclusion and exclusion criteria, justification of study population

Patient eligibility criteria

To be eligible for study participation, all patients will be required to meet the following inclusion criteria, and none of the exclusion criteria:

Inclusion criteria

1. Suspicion of community acquired pneumonia (CAP) or nursing-home acquired pneumonia consulting to the ED
2. Age>65 years
3. Signed informed consent
4. Presence of at least one respiratory symptom (new or increasing cough or dyspnoea, purulent sputum, pleuritic chest pain, respiratory rate >20/min, focal auscultatory findings

or oxygen saturation <90% on room air)

5. and at least one sign or laboratory finding compatible with an infection (temperature $>37.8^{\circ}\text{C}$ or $<36.0^{\circ}\text{C}$, CRP $>10 \text{ mg/L}$, PCT $>0.25\mu\text{g/L}$, leukocyte count $>10\text{G/L}$ with $>85\%$ neutrophils or band forms) will be required
presence of acute delirium or unexplained acute fall can substitute for the presence of either the respiratory or the infectious symptom in patients older than 80 years

Exclusion criteria:

1. Need for an immediate admission to the intensive care unit (ICU)
2. Diagnosis of pneumonia in the past 3 months
3. SARS CoV-2 infection diagnosed by PCR or antigenic test within the past 3 weeks and before the arrival to the ED
4. Transfer from another hospital with a diagnosis of pneumonia
5. Thoracic CXR or CT scan or US already performed during the present episode
6. Need for an immediate contrast-enhanced CT
7. Advanced care planning limiting therapy to comfort care only
8. Prisoners
9. Known uncontrolled psychiatric disorders
10. Previous enrollment into the current study

Reasons for inclusion of vulnerable participants:

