4.4 Withdrawal and discontinuation

Withdrawal:

If a patient wishes to withdraw consent, the investigator will be informed, and the patient will be excluded from the study without any consequence on his care.

As the validity of the clinical trial or its results could be distorted in essential points by the destruction of biological material and personal health-related data, their use in the clinical trial will be allowed despite the refusal of the patient. Since pneumonia is very frequent in elderly patients and since this population is very rarely included in clinical trials, we think it is very important to carry out this trial and not to destroy data which would be valuable for further elderly patients having pneumonia.

In case of protocol violation, the patient will stay in the randomized arm for the intention to treat analysis and will be excluded from the arm for the per protocol analysis. If the patient gets lost to follow-up, the data will be censored after the last visit. In case of death, the civil registry will be consulted regarding the information on mortality.

Death of the patient:

In case of death before obtaining provisional consent, there will be no inclusion.

In case of death of the person after provisional consent, it will be verified whether the patient has issued Advance Directives authorizing the use of data or biological materials for research purposes. If this is not the case, the consent of the representative will be necessary.

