5. STATISTICS AND METHODOLOGY

5.1. Statistical analysis plan and sample size calculation

Methodology

[name]; Investigation Unit, Geneva University Hospitals, [name], Switzerland, Email: [contact], [contact]

We hypothesize that the proportion of patients with a correct diagnosis of pneumonia (proportion of true positive plus true negative) will be higher in LDCT arm than in CXR arm. The null hypothesis that will be tested in the primary analysis is the equality of proportion of correctly classified patients in LDCT and CXR arm.

The analysis will follow the intention to treat principle. A sensitivity analysis will be conducted on the per protocol population (i.e. excluding patients who have not received the allocated intervention, and patients who crossed over). Another sensitivity analysis will be conducted excluding patients who will have had CXR before LDCT and LUS.

The diagnosis made by the panel of experts will be the reference diagnosis for calculation of the primary outcome in each arm, and to determine diagnostic accuracy expressed as sensitivity, specificity, predictive values and likelihood ratios. The primary outcome in each arm will be compared to the two other ones.

Primary analysis

The reference diagnosis will be positive (respectively “negative”) if the panel of experts rates the probability of pneumonia diagnosis “intermediate” or “high” (respectively “low”) on the Likert scale. The clinician’s diagnosis will be positive (respectively “negative”) if the clinician rates the probability of pneumonia diagnosis “intermediate” or “high” (respectively “low”) on the Likert scale. We will assume an adequate diagnosis classification, if the clinician’s diagnosis and the reference diagnosis (panel of experts) agree (true positive and true negative diagnoses). The proportions of correctly classified patients in the LDCT and CXR arms will be calculated with 95% Clopper-Pearson confidence intervals (CIs), and will be compared with a logistic regression model adjusted for sites to account for the stratified randomization. The statistical test will be two-sided and the significance threshold will be 0.05.

Secondary analyses

1) The proportion of adequate diagnoses in the LUS arm will be also calculated with the 95% Clopper-Pearson CI, and will be compared with the CXR arm using a logistic regression model adjusted for sites.

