**Note: If an event is reported at multiple follow-up visits, the earliest available date will be used for analysis.**

## 8.2 Analysis methods

If not otherwise stated, the analyses will be performed on the full analysis set.

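### The SAP removes randomised patients with eligibility violations from the primary analysis set, whereas the protocol keeps violators in their randomised arm; the change is not declared.

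*SAP*

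**What the plan says.** Protocol 5.1 states: "The analysis will follow the intention to treat principle". Protocol 4.4 adds: "In case of protocol violation, the patient will stay in the randomized arm for the intention to treat analysis"; such a patient is excluded only from the per-protocol analysis.

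SAP 4.2 describes its full analysis set (FAS) as "as close as possible to the intention-to-treat ideal of including all randomised subjects". SAP 4.2.1 then lists three grounds for removing a randomised patient. The first is "the failure to satisfy major entry criteria (eligibility violations". The other two, no trial exam and no data after randomisation, are not at issue here. SAP 8.2 says: "If not otherwise stated, the analyses will be performed on the full analysis set". The primary analysis in SAP 8.2.2.1 names no other set.

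SAP Section 9 is where departures from the protocol are declared. It lists in-hospital mortality, two added subgroups and the dropped time to clinical stability. It does not mention the analysis set.

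The SARS-CoV-2 exclusion also varies in wording. Protocol 4.1 has "SARS CoV-2 infection diagnosed by PCR or antigenic test within the past 3 weeks and before the arrival to the ED", and the background part of the synopsis agrees with it. SAP 6.1 has only "SARS CoV-2 infection diagnosed by PCR or antigenic test within the past 3 weeks". The list of exclusion criteria in the protocol synopsis also lacks the limit to diagnoses made before arrival.

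**The concern.** Removing patients after randomisation for an eligibility failure is harmless to the comparison only if the decision cannot depend on arm or outcome. The usual safeguards are a closed list of objective criteria, a judgement based on data fixed before randomisation, and assessors who are blind to arm and outcome. The SAP states none of these. It does not say which entry criteria are major, and the only predefined major deviation in SAP 5 is broken masking of the concealed images. It names nobody to judge eligibility. SAP 5 allows deviations to be identified retrospectively, and SAP 1 says the document was finalised after enrolment. By then the concealed images have been in the health record since day 5 (Protocol 4.3) and outcomes are known.

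Many entry criteria are plain facts. Some need judgement, such as the suspicion of pneumonia or the need for an immediate contrast-enhanced CT. At least one differs between passages: delirium or a fall may substitute for a symptom from age 80 in the protocol synopsis, but only above 80 in Protocol 4.1 and SAP 6.1. If exclusions on such grounds fall unevenly between arms, the primary difference is biased and the benefit of randomisation is partly lost.

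**Working it through.** **Which rule governs the primary analysis**

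| Question | Protocol | SAP |
|---|---|---|
| Principle | Intention to treat (5.1) | FAS, described as near to it (4.2) |
| Violators in the primary set | Stay in the randomised arm (4.4) | Eligibility violators removed (4.2.1) |
| Where violators are dropped | Per protocol only (4.4) | Already dropped from the FAS |
| Change declared | – | Not in Section 9 |

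The SAP is not uniform either: 8.2.3.4 analyses length of stay and ICU/IMCU transfer among all randomised patients.

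**The plan's own figure.** Inputs from SAP 3.5: accuracy 68% (CXR) and 84% (LDCT), two-sided alpha 0.05, power 90%. With pooled variance and mean proportion 0.76:

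n = [1.960·√(2·0.76·0.24) + 1.282·√(0.68·0.32 + 0.84·0.16)]² / 0.16² = 148 per arm.

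This reproduces the stated 150 closely. Power at 150 is 0.904, and 165 = 150 × 1.10.

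**Effect on power.** After the planned 10% loss, 165 × 0.90 = 148.5 per arm and power is 0.902. The number of violators is not in the documents. Assuming a further 2%, 5% or 10% removed:

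- 2%: n = 145.5, power 0.896
- 5%: n = 141.1, power 0.886
- 10%: n = 133.7, power 0.869

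The loss is small.

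**Effect on the difference.** If a fraction f of an arm with accuracy p is removed, and accuracy among those removed is a, the arm's accuracy moves by

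(p − f·a)/(1 − f) − p = [f/(1 − f)]·(p − a).

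Take f = 5% and a = 60%, both assumed:

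- LDCT: (0.84 − 0.03)/0.95 − 0.84 = 0.0126, or 1.26 points.
- CXR: (0.68 − 0.03)/0.95 − 0.68 = 0.0042, or 0.42 points.

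Three scenarios follow:

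1. Removed from LDCT only: the difference rises by 1.26 points, about 1.3.
2. Removed from both arms, accuracy 60% in each: 1.26 − 0.42 = 0.84 points, about 0.8.
3. Removed from both arms, each 24 points below its own arm's accuracy (60% in LDCT, 44% in CXR): CXR moves by (0.05/0.95)·0.24 = 1.26 points as well, so the net shift is 0.

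For f from 2% to 10% and a from 50% to 70%:

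- LDCT only: from (0.02/0.98)·0.14 = 0.3 points to (0.10/0.90)·0.34 = 3.8 points.
- Both arms with the same a: the net is [f/(1 − f)]·0.16 whatever the value of a, so 0.3 to 1.8 points.

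In scenario 2 those removed show no LDCT benefit, so part of that shift is a change of population rather than selection bias. Scenario 1 is the one that threatens validity.

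**The case against.** Several objections carry weight.

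- Protocol 4.4 speaks of protocol violations in a section on withdrawal, and the per-protocol exclusions in Protocol 5.1 concern patients who did not receive the allocated exam or crossed over. One can argue that eligibility failures were not in mind. This softens the conflict but does not remove it, since neither section makes an exception for them.
- A FAS that omits eligibility failures can be acceptable when the criteria are objective, fixed before randomisation and judged alike in all arms. The SAP does not set those conditions.
- Protocol 4.3 says investigators are blinded to arm and data go to a blinded assessor and analyst with coded labels. SAP 5 has deviations summarised by arm, so an imbalance would be visible. These help, but nothing ties the eligibility decision to the blinded process.
- Entry criteria precede allocation, so similar exclusion rates in all arms are the natural expectation. This stands, and it is why the one-arm figures are an upper case.

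A reader might go further and infer that SAP 6.1 turns patients who test positive for SARS-CoV-2 in the ED into violators and empties the SARS-CoV-2 subgroup. The documents do not support that. SAP Table 1, titled for the FAS, has a row for SARS-CoV-2 positive patients; SAP 8.2.2.6 plans the subgroup; and the statistical part of the protocol synopsis counts SARS-CoV-2 among the viruses in its PCR subgroup. The short wording is also in the synopsis exclusion list, so it is not peculiar to the SAP.

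**Conclusion.** The conflict is real and undeclared. The SAP moves into the primary set an exclusion that the protocol reserves for the per-protocol analysis, on an undefined criterion and without a stated blind process. This should be corrected before the analysis.

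The likely size is modest: about 1.3 points if 5% with 60% accuracy leave the LDCT arm only, about 0.8 points if both arms lose them, and zero if the accuracy deficit is equal. Both the 5% and the 60% are assumptions. The 3.8-point extreme needs 10% removed from one arm only and should not be read as an expected bias.

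Nor do the documents say that eligibility will be re-judged in the light of images or outcome. They only leave room for it. The SARS-CoV-2 wording is a secondary point of consistency, not evidence that patients will be lost.

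**What to change.** 1. In SAP 4.2.1 and 8.2.2.1, base the primary analysis on all randomised patients whose data may be used under the consent rules in Protocol 4.4 and 8.4, in their allocated arm. Apply the complete-case rule of SAP 8.4 where the clinician rating or the reference diagnosis is missing.
2. Make the exclusion of eligibility violators a sensitivity analysis. List the criteria that count as major, and have violations judged on pre-randomisation data by someone blind to arm and outcome.
3. If the sponsor prefers to keep the current FAS as primary, the least that is needed is that definition, the blind review and an entry in SAP Section 9.
4. Reconcile the SARS-CoV-2 exclusion across the protocol synopsis (background and exclusion list), Protocol 4.1 and SAP 6.1, so that no reading of SAP 6.1 makes patients diagnosed in the ED violators.

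The cost is wording only. A few ineligible patients stay in the primary set and may slightly dilute the effect; the sensitivity analysis will show by how much. Requiring both ratings still conditions on data obtained after randomisation, so missing ratings should be reported by arm, as SAP 8.4 already plans.
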